3.0 Setting

Four medical centers in Detroit (Henry Ford Hospital, Detroit Receiving Hospital, Sinai Grace Hospital, and Harper University Hospital) with a single coordinating center (Wayne State University). The emergency departments of these two hospitals treat >100,000 patients annually each. The patient population is majority African American. This makes a perfect setting to execute the proposed study. In addition, both hospitals are affiliated with Wayne State University, which has a highly functional Clinical Research Service Center that is under the direction of one of the co-investigators ([name]), enabling facilitated outpatient follow-up.

4.0 Eligibility Criteria

Inclusion Criteria:

- 1) Age >18 and <90.
- 2) Established HF with reduced ejection fraction (EF ≤35 %), assessment done within 12 months of index visit.
- 3) Admitted to the observation unit or inpatient ward for management of AHF.
- 4) Heart rate ≥70 beats per minute, with sinus rhythm.
- 5) Receiving guideline based medical therapy in the judgement of the treating physician.
- 6) Patient currently on a Beta Blocker regimen.
- 7) Achieved clinically determined stabilization during treatment under observation unit or during hospital admission within 48 hours from the time of admission.

Exclusion Criteria:

- 1) Known intolerance to study drug.
- 2) End stage renal disease.
- 3) Plan to titrate BB at the time of discharge from the observation unit.
- 4) Any condition that in the opinion of the investigators will interfere with the ability to complete the study (e.g. history of extreme non-adherence, extreme psychosocial instability).
- 5) Inability to provide written informed consent.
- 6) Pregnant or nursing (lactating) women, where pregnancy is defined as the state of a female after conception and until the termination of gestation, confirmed by a positive hCG laboratory test (women of childbearing age will be included only if they agree to use adequate contraceptive methods or engage in sexual abstinence).
- 7) Systolic Blood pressure less than 100 mmHg.
- 8) Sick sinus syndrome, sinoatrial block or 3rd degree AV block, unless a functioning demand pacemaker is present.

- 9) Severe hepatic impairment.
- 10) Pacemaker dependence (i.e. heart rate maintained exclusively by the pacemaker).
- 11) Concomitant use of strong CYP3A4 inhibitors. Examples of strong CYP3A4 inhibitors include azole antifungals (e.g., itraconazole), macrolide antibiotics (e.g., clarithromycin, telithromycin), HIV protease inhibitors (e.g., nelfinavir), and nefazodone.
- 12) Concomitant use of diltiazem or verapamil that are not planned for discontinuation.
- 13) Severe, left sided valvular abnormalities (severe aortic stenosis, severe mitral stenosis, severe aortic insufficiency or severe mitral regurgitation).
- 14) Documented, prior to or at the time of randomization, restrictive amyloid cardiomyopathy, or acute myocarditis, or hypertrophic obstructive, restrictive, or constrictive cardiomyopathy.

[figure not shown]
5.0 Endpoints

Efficacy:

- Primary - Change in heart rate (Day 28 (+/-2) - baseline), measured by 12-lead ECG and Zio® patch (Day 14 (+/-1) - baseline).
- Secondary - Change in heart rate in self-identified African Americans (Day 28 (+/-2) – baseline), measured by 12-lead ECG and Zio® patch³(Day 14 (+/-1) - baseline).
- Exploratory:
 - 1) Change in NT-proBNP (Day 28 (+/-2) – baseline)
 - 2) Change in hs-cTnT (Day 28 (+/-2) – baseline)

Safety: Presentation for unplanned medical care in any setting within 28 (+/-2) days.

6.0 Study Design & Timeline

7.0 Post-Discharge Management

Subjects will be enrolled at the time of discharge from the hospital or observation unit (visit 1), all baseline procedures will be performed at this time, these would include blood draw for biomarker assessments, vitals, physical examination, Zio patch³ placement and IP dispensation. At the baseline visit, the study team will schedule a follow-up appointment post Day 28 +/- 2 (Visit 3) with the subject's primary care physician(PCP)/cardiologist, if the subject does not have their own PCP/cardioologist the study team will schedule and facilitate this appointment with the Gateway Clinic. A list of current medications and doses will be provided. At Day 14 +/- 1 (visit 2) the subject will return for a follow up visit for IP accountability and titration (if needed), BB uptitration (if needed), collection of the HR monitor (Zio patch³), assessment of any adverse events, ECG, vital signs, and will undergo a physical examination. At Day 28 +/- 2 (visit 3), the patient will return for study exit procedures, which include blood draw for biomarker assessments, vitals, physical examination, assessment of adverse events (if any), and IP return.

As with any clinical trial, no un-blinding will occur unless there is a concern for patient safety, as this could affect the integrity of data. We will provide the patient and their PCP/cardioologist a clinical summary, inclusive of ECGs. On-going management for the patient's condition will be at the discretion of their PCP/cardioologist and will not be influenced directly by participation in this study.

8.0 Schedule of Events

	Baseline - Visit 1 ^a	Day 14 (+/- 1) - Visit 2	Day 28 (+/- 2) - Visit 3
Screening (I/E)	X		
Informed consent	X		
Medical History	X		
Medication History	X		
Concomitant Medications	X	X	X
Physical Exam	X	X	X
Vitals, including Height and Weight	X	X	X
12-lead ECG	X	X	X
Zio [®] XT patch HR monitoring	X	X	
Echocardiogram	X ^b		
Biomarker Assessment (NT-proBNP and hs-cTnT)	X		X
Urine Pregnancy Test	X		
Randomization	X		
IP Dispensation	X		
IP Titration (if needed)		X	
IP Accountability		X	X
Beta Blocker uptitration (if needed)		X	
Assessment of AEs	X	X	X

^aBaseline procedures will be done at discharge from the hospital or observation unit.

^bAssessment done at index visit or within 12 months of index visit.

9.0 IP Dosage and Titration

At Randomization the initial Ivabradine dose will be 5 mg BID. If at any time during the study the patient's HR <50 AND suggestive symptoms such as lightheadedness or hypotension are present: Discontinue study drug immediately.

At Day 14 (+/-1) follow up, medication adjustments will be made based on the following criteria:

- 1) If patient has signs or symptoms of continued volume overload diuretic dose will be doubled for 3 days and vasodilators (ACEi/ARB/H+N) reassessed for potential increase, and BB continued at current dose. Regarding IP:
 - a. If HR <50 bpm decrease study dose by 2.5 mg BID.
 - b. If HR between 50-60 AND possible signs/symptoms of bradycardia (i.e. light headedness or hypotension), decrease study dose by 2.5 mg BID.
 - c. Otherwise (i.e. neither above criteria present) no adjustment to study drug.
- 2) If patient appears stable and euvolemic:
 - a. If HR >60 bpm and patient on target BB dose (i.e. total daily of 50mg carvedilol OR 200mg metoprolol succinate OR 10mg Bisoprolol): Increase study drug dose by 2.5 mg BID, to the maximum dose of 7.5 mg BID.
 - b. If HR >60 bpm and patient receiving less than target BB dose: Double BB daily dose.
 - c. If HR 50-60 bpm: Maintain study drug dose at 5 mg BID (and no BB change).
 - d. If HR <50 bpm: Decrease study drug by half (2.5 mg BID). If IP is at the lowest dose i.e. 2.5mg BID, it will be stopped.

At Day 28 (+/-2) follow up, IP will be permanently stopped and no unblinding will occur unless for safety reasons. Other medications dose adjustments (if needed) will be made according to standard of care practice (GDMT).

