2.0 Rationale

Ivabradine (IVA) has been shown to decrease the risk of hospitalizations for worsening HF and was associated with a trend towards improved mortality in the SHIFT¹ trial. SHIFT¹ excluded patients within 4 weeks of hospital discharge, so the efficacy and safety of IVA in this setting is less clear. In today's health care environment more and more patients that present to the ED for mild AHF are being placed into observation unit and subsequently discharged, or discharged outright from the ED. This is not only a growing segment of patients, but also represents an important window of opportunity to intervene with a potentially effective therapy.

Moreover, at this point in a patient's experience (being discharged after getting treated for exacerbation of HF), it's not clear that beta blockers (BB) should yet be increased/started due to the recent state of exacerbation. Standard treatment of worsened heart failure presenting to the ER or urgent care includes diuresis and vasodilators (e.g. ACE-I), but according to usual standard of care, titration of beta blockade is often reserved for outpatient follow up after a period of demonstrated stability (in the ambulatory setting). This is in contradistinction to hospitalized patients, where patients have been observed by the treating team for days, presumably show stability and improvement, and starting low dose BB at the time of hospital discharge has been shown to be safe (IMPACT-HF² trial). As such these ED/Observation discharge patients are often not optimal candidates for intensification of BB at the time of release, and could be considered to be at maximally tolerated BB dose (for at least for 2-4 weeks). This may represent a vulnerable period for these patients; it's unknown in the setting of Observation discharge but evidence from hospitalized patients indicates that the highest daily risk of rehospitalization is in the days just after discharge. IVA may be effective post observation unit management (where lower risk HF patients are typically placed), to reduce heart rate (without decreasing contractility, such as a BB would) to help reduce the risk of hospitalization or emergency care, but safety and efficacy (in terms of heart rate lowering) in this setting has not been previously explored.

Additionally, the SHIFT¹ trial lacked African Americans and this unique patient population has not been previously studied with IVA. The investigating sites serve a predominantly African American patient

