10.0 Beta Blockers Dosage and Titration

Subjects will be assessed for BB therapy uptitration at Day 14 (+/-1) follow up.

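### The Day 14 rule for doubling the beta blocker has no ceiling, so starting doses between half of target and target end above the protocol's own target

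*Protocol*

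**What the plan says.** Protocol section 9.0 sets the medication changes for the Day 14 visit. Among stable, euvolemic patients with heart rate above 60 bpm it separates two groups.

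- Rule 2a covers those already at target: "If HR >60 bpm and patient on target BB dose (i.e. total daily of 50mg carvedilol OR 200mg metoprolol succinate OR 10mg Bisoprolol"). Their study drug goes up by 2.5 mg twice daily, "to the maximum dose of 7.5 mg BID".
- Rule 2b covers those below target: "If HR >60 bpm and patient receiving less than target BB dose: Double BB daily dose". The instruction ends there.

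Other places deal with beta blocker dosing, but none gives a maximum for Day 14.

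- Section 10.0, the section on beta blocker titration, is one sentence on timing: "Subjects will be assessed for BB therapy uptitration at Day 14 (+/-1) follow up".
- The schedule in section 8.0 lists "Beta Blocker uptitration (if needed"), and section 7.0 has the same qualifier.
- The standard-of-care sentence in section 9.0, "Other medications dose adjustments (if needed) will be made according to standard of care practice (GDMT"), belongs to the Day 28 visit.
- Section 4.0 requires only "Patient currently on a Beta Blocker regimen", with no limit on agent or dose.
- The SAP does not discuss beta blocker dosing.

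**The concern.** Rule 2a gives the study drug a ceiling. Rule 2b, on the next line, gives the beta blocker none, although the target that would serve as one has just been defined. Doubling is harmless to the target for a patient far below it, but not for a patient close to it.

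Two things are at stake. Staff who apply the sentence exactly would prescribe more than the protocol's own target to a patient who is also taking blinded study drug (ivabradine or, under 1:1 allocation, placebo in about half of the planned patients). And the dose depends on the reader: a patient on 150 mg of metoprolol succinate leaves the visit on 300 mg if the rule is taken literally, or on 200 mg if a ceiling is inferred.

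**Working it through.** The plan states no figure on this point to reproduce. The check is whether, and where, doubling passes the target.

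**Inputs.** Targets T from rule 2a: carvedilol 50 mg, metoprolol succinate 200 mg, bisoprolol 10 mg, all total daily doses. Action from rule 2b: a daily dose D below T becomes 2D. The starting doses below are illustrations, because the available text gives no distribution of baseline doses.

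**Condition for overshoot.** Rule 2b applies when D < T. The new dose exceeds target when 2D > T, that is, when D > T/2. So every dose with T/2 < D < T overshoots, and no dose with D ≤ T/2 does. Since D < T, the new dose is always below 2T.

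**Bands affected (daily dose).**

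| Drug | T/2 | T | Starting dose that overshoots | Dose after rule 2b |
|---|---|---|---|---|
| Carvedilol | 25 mg | 50 mg | above 25, below 50 mg | above 50, below 100 mg |
| Metoprolol succinate | 100 mg | 200 mg | above 100, below 200 mg | above 200, below 400 mg |
| Bisoprolol | 5 mg | 10 mg | above 5, below 10 mg | above 10, below 20 mg |

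**Boundary check at D = T/2.** 2 × 25 = 50, 2 × 100 = 200 and 2 × 5 = 10 mg. Each lands exactly on target.

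**Examples, as written and with a cap.** The excess is 2D − T, the ratio is 2D/T, and the capped dose is min(2D, T).

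| Start | As written | Ratio to target | Excess | Capped | Capped step T/D |
|---|---|---|---|---|---|
| Carvedilol 37.5 mg | 75 mg | 75/50 = 1.50 | 25 mg | 50 mg | 50/37.5 = 1.33 |
| Metoprolol succinate 125 mg | 250 mg | 250/200 = 1.25 | 50 mg | 200 mg | 200/125 = 1.60 |
| Metoprolol succinate 150 mg | 300 mg | 300/200 = 1.50 | 100 mg | 200 mg | 200/150 = 1.33 |
| Metoprolol succinate 175 mg | 350 mg | 350/200 = 1.75 | 150 mg | 200 mg | 200/175 = 1.14 |
| Bisoprolol 7.5 mg | 15 mg | 15/10 = 1.50 | 5 mg | 10 mg | 10/7.5 = 1.33 |

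**Could another sentence supply the ceiling?** The if-needed qualifier in sections 7.0 and 8.0 governs whether to raise the dose, not how far. Section 10.0 fixes when the assessment happens. The standard-of-care sentence applies at Day 28, two weeks after the doubling. None of them limits the Day 14 dose.

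**Sample size.** Section 14.0 uses a difference of 8 bpm, a standard deviation of 13 bpm, 90% power and a two-sided 0.05 level. These give 56.5, rounded up to the stated 57 per group. Beta blocker dose is not an input, so the calculation does not depend on rule 2b.

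**The case against.** The best defence is that the ceiling is implied. Rules 2a and 2b read as a pair: target is the point where beta blocker escalation stops and study drug escalation starts. A clinician would have to pass a target defined one line earlier, and nothing in the documents shows that anyone did. Overshoot also needs an intermediate starting dose; regimens that move by simple doubling, such as 12.5, 25 and 50 mg of carvedilol, never reach it. This stands as a statement of intent and limits the reach of the point. It does not supply the missing maximum.

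The surrounding protections are also real. Rule 2b applies only to stable, euvolemic patients with heart rate above 60 bpm. Volume-overloaded patients keep their current beta blocker dose, and those at 50-60 bpm have no beta blocker change. Vital signs, ECG and examination are done at Day 14 and again at Day 28. Section 11.0 provides a telephone line that can lead to an unscheduled visit. Study drug is stopped for a heart rate below 50 bpm with suggestive symptoms, and for listed adverse events.

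A reader might infer that the Rationale contradicts rule 2b, since it says these patients "could be considered to be at maximally tolerated BB dose (for at least for 2-4 weeks"). The documents do not support that. The passage concerns intensifying the beta blocker at release from the emergency department or observation unit; it does not address doses above target.

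**Conclusion.** The point holds as a minor error in a dosing rule. For the three drugs in rule 2a, a literal reading takes every starting dose strictly between half of target and target past target, by a factor above 1 and below 2. Doses at or below half of target are unaffected. This follows from the rule's wording and the 2a targets alone. It does not extend to other beta blockers, which section 4.0 admits but for which the protocol states no target.

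Three stronger readings are tempting and not supported.

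- **That patients were harmed or exposed to a known danger.** The documents do not show that a dose above these targets causes harm.
- **That many patients were affected.** The number in the band is unknown and may be zero.
- **That the primary result is biased.** Rule 2b is triggered by heart rate after randomisation and acts before the Day 28 heart-rate measurement. Placebo patients would be likelier to meet it if ivabradine lowers heart rate, so an effect of the extra dose on the endpoint cannot be ruled out. Its size is unknown and probably small, and the documents give no means of estimating it. It would be equally unsupported to say that the primary test is untouched.

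The SAP reports 19 of the targeted 132 patients and no completed formal analysis, so the point matters mainly if the protocol is reused.

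**What to change.** In any reuse of the protocol, word the action in rule 2b as: *Double the BB daily dose, not to exceed the target total daily dose in 2a; for a beta blocker not listed in 2a, not to exceed a maximum specified by the sponsor's clinicians.* The clinicians should also confirm that the 2a target is the ceiling they want for the listed drugs. The second clause is needed because a cap tied to 2a alone would leave unlisted agents open-ended.

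The cost is one sentence in section 9.0 and a clinical decision on unlisted agents, with no added visits, tests or patients. The downside is a smaller dose step for patients in the band: 150 mg of metoprolol succinate rises to 200 mg instead of 300 mg. For the listed drugs, patients at or below half of target are treated exactly as now. The change cannot alter care for the 19 patients in the final cohort.

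### At Day 14 a euvolemic patient at HR 50–60 with mild light-headedness has no written step-down, although an overloaded patient with the same symptom does

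*Protocol*

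**What the plan says.** Protocol Section 9.0 starts every patient at one dose: "At Randomization the initial Ivabradine dose will be 5 mg BID". The Day-14 visit then splits patients by volume status.

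- **Branch 1, continued volume overload.** Rule 1a steps down at HR below 50. Rule 1b adds "If HR between 50-60 AND possible signs/symptoms of bradycardia (i.e. light headedness or hypotension), decrease study dose by 2.5 mg BID". Rule 1c closes the branch: "Otherwise (i.e. neither above criteria present) no adjustment to study drug". At the same visit the diuretic is doubled for three days and vasodilators are reviewed for a possible increase.
- **Branch 2**, entered under the words "If patient appears stable and euvolemic". Above 60 bpm, either study drug or beta-blocker goes up (2a, 2b). In the middle band, rule 2c says "If HR 50-60 bpm: Maintain study drug dose at 5 mg BID (and no BB change". Below 50, rule 2d says "If HR <50 bpm: Decrease study drug by half (2.5 mg BID". There is no closing catch-all.

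Two stopping rules sit over both branches. Section 9.0 has an any-time stop: "HR <50 AND suggestive symptoms such as lightheadedness or hypotension are present: Discontinue study drug immediately". Section 11.0 stops study drug, whatever the heart rate, for treatment-emergent clinically relevant events; its open-ended list includes hypotension and significant dizziness. A drug stopped under Section 11.0 is not restarted.

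**The concern.** Rule 1b shows that the authors regarded possible light-headedness or hypotension at HR 50–60 as enough reason to lower the dose without stopping it. Rule 2c covers the same heart-rate band and does not ask about symptoms. A mildly symptomatic euvolemic patient then gets either no change or, if the investigator judges the event clinically relevant, an irreversible stop. The intermediate dose of 2.5 mg BID already exists in that branch, but only for HR below 50.

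The stakes are tolerability for about two weeks and, for some patients, the chance to stay on study drug to Day 28 rather than stop for good.

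**Working it through.** No sample-size or power figure in the plan depends on this point, so the main check is a reading of the rules side by side.

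**Decision grid at Day 14, HR 50–60, patient on 5 mg BID**

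| Volume status | Symptoms | Written action | Source |
|---|---|---|---|
| Overloaded | None | No change | 1c |
| Overloaded | Possible light-headedness, short of a Section 11.0 event | 5 to 2.5 mg BID | 1b |
| Euvolemic | None | Hold 5 mg BID | 2c |
| Euvolemic | Possible light-headedness, short of a Section 11.0 event | Hold 5 mg BID, or no rule | 2c, or gap |
| Either | Clinically relevant hypotension or significant dizziness | Permanent stop | Section 11.0 |

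Without symptoms the two branches agree. With a clinically relevant event they also agree. They differ only in the mildly symptomatic rows.

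**Can another rule fill the euvolemic symptomatic cell?**

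1. Rule 2d requires HR below 50, so it does not reach the band.
2. The any-time stop in Section 9.0 also requires HR below 50.
3. Branch 1 requires signs or symptoms of volume overload, so a euvolemic patient cannot enter it.
4. Section 11.0 can be applied at any heart rate, but it offers a stop and not a reduction.
5. If stable excludes symptomatic patients, branch 2 does not apply either, and branch 2 has no counterpart to 1c.

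**Dose difference in that cell**

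- Under 2c: 2 × 5 = 10 mg/day. After a step-down as in 1b: 2 × 2.5 = 5 mg/day. Difference: 5 mg/day.
- Day 14 to Day 28: 5 × 14 = 70 mg.
- Shortest interval the visit windows allow, Day 15 to Day 26: 5 × 11 = 55 mg. Longest, Day 13 to Day 30: 5 × 17 = 85 mg.

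**Why no patient count follows**

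A count needs the entry heart rates, the share euvolemic at Day 14 and the rate of mild symptoms. The documents give none of these. Even the first step moves widely. Take the change assumed in Section 14.0 (mean −8, SD 13 bpm), assume a common entry heart rate h and normality, and apply the change at Day 14. The share in the band is Φ((60 − h + 8)/13) − Φ((50 − h + 8)/13):

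- h = 70 (the eligibility floor in Section 4.0): Φ(−2/13) − Φ(−12/13) = 0.261
- h = 80: Φ(−12/13) − Φ(−22/13) = 0.133
- h = 90: Φ(−22/13) − Φ(−32/13) = 0.038

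These shares of 4% to 26% are for all ivabradine patients in the band. Overloaded patients, those without symptoms and those stopped under Section 11.0 would still have to be removed.

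**The case against.** The strongest reply is that the symptom condition already sits in the branch heading. Branch 2 requires stability as well as euvolemia, and if stability meant only volume status the second word would be enough. Symptomatic patients below 50 bpm are already removed by the any-time stop, so rule 2d governs only asymptomatic ones, which fits a symptom-free reading. On that reading 2c holds no symptomatic patient at 5 mg BID. This is a fair reading and the text does not exclude it. It changes the form of the gap but does not close it, because the euvolemic symptomatic patient then has no Day-14 rule at all.

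Second, Section 11.0 handles the serious cases, and its open list lets an investigator act on lesser ones. That stands, and it confines the point to milder symptoms. It does not supply a step-down.

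Third, the branches are different clinical situations. Doubling the diuretic and possibly raising vasodilators can lower blood pressure, so more caution with study drug in branch 1 is coherent. This justifies part of the asymmetry. It does not say what to do with the euvolemic patient, and rule 1b itself gives bradycardia symptoms as its reason.

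A reader might also infer more than the documents support:

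- *That branch 1 steps down at HR 50–60 in general.* It does so only with possible symptoms; otherwise 1c and 2c both leave the dose alone.
- *That patients with clinically relevant hypotension are kept on drug.* Section 11.0 stops them.
- *That the heart-rate comparison is biased.* Nothing in the documents shows this.

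**Conclusion.** The point holds as a minor gap in the dosing rules. At HR 50–60, a euvolemic patient with mild light-headedness short of a Section 11.0 event is either held at the starting dose or covered by no Day-14 rule, and the only other written action is a permanent stop. This follows from the text under either reading of stable.

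The dose at issue is 5 mg/day, 70 mg over the planned 14 days (55 to 85 mg across the windows). The number of patients is likely small but cannot be estimated from the documents; any figure would rest on an unsourced symptom rate. The SAP reports 19 patients enrolled, 13 of them on ivabradine, and no formal analysis, so the practical value now lies in any reuse of this titration scheme.

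**What to change.** Replace rule 2c with: *HR 50–60 bpm and no possible signs or symptoms of bradycardia: hold 5 mg BID, beta-blocker unchanged. HR 50–60 bpm with such signs or symptoms: step down by 2.5 mg BID, beta-blocker unchanged. Section 11.0 takes precedence for clinically relevant events.*

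The last sentence is needed because hypotension appears both as a step-down trigger in 1b and as a stopping event in Section 11.0.

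The cost is one line in Section 9.0. The 2.5 mg BID level is already used in 2d. Adverse-event assessment, ECG, vital signs and physical examination are already scheduled at Visit 2. The downside is slightly lower exposure from Day 14 to Day 28 in the patients who step down, partly offset if some of them would otherwise have stopped.
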